MedDRA	Medical Dictionary for Regulatory Activities
MITT	Modified Intention to Treat
msec	milliseconds
PEX	Perhexiline
PM	Poor metabolizer
PT	Prothrombin Time
PTT	Partial Thromboplastin Time
QTc	Corrected QT interval
QTcF	QT corrected according to Fridericia's formula
RBC	Red Blood Cells

SAE	Serious adverse event
SAP	Statistical Analysis Plan
TE	Treatment-Emergent
TEAE	Treatment-Emergent Adverse Event
TRANS	trans -Hydroxy-Perhexiline
ULN	Upper limit of normal
UM	Ultra-rapid metabolizer
VO ₂ MAX	Maximal oxygen consumption

1 INTRODUCTION

The purpose of this document is to provide a description of the statistical methods and procedures to be implemented for the analysis of data from Heart Metabolics, HML-PHX-005. This document is based on protocol version 11, 02 December 2016. If circumstances arise during the study such that more appropriate analytic procedures become available, this statistical analysis plan (SAP) may be revised. Any revisions to the SAP (both alternative and additional methods) will be made prior to database lock and reasons for such revisions will be described in the final Clinical Study Report (CSR).

2 OVERVIEW

2.1 Objectives

2.1.1 Primary Objective

The primary objective of the study is to evaluate the effect of PEX on the change from Baseline of maximal oxygen consumption (VO_{2MAX}) in patients with hypertrophic cardiomyopathy (HCM) and moderate-to-severe heart failure with preserved left ventricular (LV) function following repeat dosing with PEX for 112 days.

2.1.2 Secondary Objectives

The secondary objectives of the study are to evaluate:

- The ascending dose-response effect on the change from Baseline of VO_{2MAX} in patients with HCM and moderate-to-severe heart failure with preserved LV function following repeat dosing with PEX for 112 days.
- The electrocardiographic (ECG) response, tolerability and safety of orally administered PEX in patients with HCM and moderate-to-severe heart failure with preserved LV function following repeat dosing with PEX for 112 days.

2.2 Study Design

This Phase 2, open-label, single arm study aims to confirm the optimal dosing regimen of PEX for use in a future phase 3 study. The study had planned to enroll approximately 33 patients with HCM from approximately 7-10 study sites in the US.

In the 28 days before the planned start of study dosing, each patient was to be screened for eligibility. A complete list of all eligibility criteria is available in section 4.2 and 4.3 of the study protocol.

[figure not shown]
Following screening, a patient's suitability to enter the study was to be confirmed at the Baseline assessment. Confirmation would include an evaluation of the patient's Baseline 12-lead ECG by a central assessor from ECG Corelab. Study medication was only to be dispensed after confirmation of the patient's suitability to enter the study. Any delays in the central assessment of

the Baseline ECG could result in the patient having to return to the site for study drug dispensing and having a Baseline assessment split over more than one day. The day that study drug dosing commenced was to be regarded as Day 1.

Patients who met the study inclusion and exclusion criteria were to be admitted to the study on the morning of Day 1 when they were to start their open-label, study-drug dosing regimen with PEX. The first dose of study drug was to be administered under the supervision of the study-site staff. Subsequent daily dosing throughout the dosing period of 112 days was to be done in the evening (preferably between 8-11p.m.).

CPEX was to be completed at Baseline (before the start of study-drug dosing on Day 1), and again at the end of Periods 1 and 2. After completion of study drug dosing (end of Period 2) there was to be a follow-up safety observation period before patients completed the study.

Figure 1 Outline Study Design

If a patient chose to withdraw from the study during the dosing phase, the site was to attempt to complete the following assessments:

- CPEX Testing and 6-Minute Walk Test
- vital signs and 12-Lead ECG
- Blood sample for PEX, CIS and TRANS, full blood cell count, routine safety serum chemistry tests, serum pregnancy test and serum levels of hemoglobin A1c
- Concomitant Medications and AEs
- Study drug accountability and treatment compliance

The total study duration for safety and efficacy follow-up was to be 24 weeks.

Complete Schedule of Protocol Activities	Screening [A]	Baseline Week 1 (Day 1) [A]	After Completion of Week 1 (Day 8)	After Completion of Weeks 2, 4, 6, 8, 10, 12 & 14 (Days 15, 29, 43, 57, 71, 85 & 99)	End of Treatment After Completion of Week 16 (Day 113)	Final Visit Week 20 (Day 140)
Time window permitted	-28 days	n.a.	±1 Day	±1 Day for Week 2 ±3 Days for other timepoints	±3 Days	±3 Days
Informed Consent	X					
Inclusion/Exclusion Criteria	X	X [B]				
Demographics, Medical Hist, Physical Exam	X					
12-lead ECG [C, D]	X	X [E]		X	X	X
CPEX Testing [D, F]	X	X [G]		After End of Week 8	X [H]	
Weight	X	X		After End of Week 8	X	X
Vital Signs [I]	X	X		X	X	X
Laboratory Procedures [J]						
Serum Pregnancy Test [K]	X					X
Urine Pregnancy Test [J, K]		X				
Serum Chemistry [L]	X			After End of Week 8	X	X
Complete Blood Count [M]	X				X	X
Coagulation Tests [N]	X					
CYP2D6 Screening [O]	X					
Plasma PEX, CIS & TRANS [P]			X	X	X	X
Biomarkers (Hemoglobin A1c)	X			After End of Week 8	X	X
Study Dosing & Dose Adjustment as per Guidelines & Algorithm [Q]		Start at 70 mg [R]	X	X		
Review of Dosing Instructions and Adherence to Dosing		X	X	X	X	
Adverse Event Assessment [S]	X	X	X	X	X	X
Adverse Device Effect Assessment [T]			X	X	X	X
Concomitant Medication Review [U]	X	X	X	X	X	X
6 Minute Walk Test (6MWT) [D]		X		After End of Week 8	X	

Footnotes:

- A. The Screening visit was to be performed within 28 days prior to dosing.
- B. Entry criteria was to be evaluated: Baseline CPEX compared to Screening CPEX, and ECG exclusion criteria
- C. ECGs were to be done in triplicate prior to blood draws when possible and obtained after the patient had been resting comfortably in a supine position for approximately 10 minutes.
- D. ECGs were to be performed first, the CPEX second, and the 6MWT last during any visit.
- E. The Baseline ECG were not to meet any of the exclusion criteria detailed in section 4.3.2; this was to be confirmed by the central ECG reader before study drug could be dispensed to the patient
- F.
 - i All CPEX test results were to be reviewed by the centralized CPEX assessor for compliance with prospectively defined CPEX test acceptance criteria
 - ii The Screening CPEX was to be performed to show that patient was able to perform exercise testing but unable to exceed 75% of the predicted age-adjusted maximum level (as determined by VO_{2MAX}).
- G.
 - i A valid Screening CPEX was to be confirmed by the centralized CPEX assessor before the Baseline CPEX was done
 - ii The Baseline VO_{2MAX} was not to vary from the screening VO_{2MAX} by more than $\pm 20\%$ (with the screening test being the reference); this was to be calculated by study-site staff in order to allow a decision on patient inclusion in the study during the Baseline site-visit
- H. If the centralized CPEX assessor deemed the EOT CPEX test to be invalid, the patient may be required to return for a repeat test.
- I. Heart rate and blood pressure assessed in the seated position after 5 minutes of rest.
- J. Samples for laboratory assays were to be sent to the central lab for analysis (with the exception of the urine pregnancy test at Baseline which were to be performed locally).
- K. Females of child bearing potential. (Eligible patients were to be advised to use an adequate contraceptive method.)
- L. Serum Chemistry: sodium, potassium, bicarbonate, chloride, calcium, phosphorus, glucose, creatinine, BUN, CPK, uric acid, albumin, total protein, total bilirubin, alkaline phosphatase, ALT (SGPT), AST (SGOT), LDH, total cholesterol
- M. CBC: hemoglobin, hematocrit, RBC, MCV, MCH, MCHC, RDW, WBC count with differential (neutrophils, bands, lymphocytes, monocytes, eosinophils, basophils), platelets.
- N. Coagulation tests: prothrombin time (PT), partial thromboplastin time (PTT), and international normalized ratio (INR).
- O. CYP2D6 Poor Metabolizer status as defined by the CPIC guidelines.
- P. All determinations of systemic blood levels of PEX, CIS, and TRANS were to be measured using the PEX-CIS assay. Blood sampling for determination of PEX, CIS and AS was to be scheduled approximately 12h after dosing on the previous study day. Results for PEX and CIS were to be reported to the study sites for confirmation of a patient's phenotypic status for PEX metabolism and for dose-adjustment decisions.
- Q. Patients were to be provided with up to 4 weeks' worth of study medication at the Baseline, Week 2, 4, 6, 8, 10, 12 and 14 study visits
- R. Study-drug was to be dispensed once the ECG Corelab confirmed that the Baseline ECG met the entry criteria. The first study-drug dose was to be administered under the supervision of the study-site staff once the study-site staff confirmed that the Baseline VO_{2MAX} was within $\pm 20\%$ of the Screening CPEX.

Note:

- i. If for any reason the ECG Corelab was not able to immediately confirm the ECG outcome, the patient was to return home without receiving any dispensed study-drug. In such cases, once the ECG Corelab confirmation became available the patient was to return to the site to collect the study drug supply. The patient was then to commence study-drug dosing (defined as Day 1).
 - ii. All Baseline ECG confirmations were to be received by study sites from the ECG Corelab within a maximum of 48h.
 - iii. Before dosing commenced; if the centralized CPEX assessor confirmed the Baseline VO_{2MAX} was not within $\pm 20\%$ of the Screening CPEX then the patient was not to enter the study
 - iv. Before dosing commenced; if the centralized CPEX assessor confirms an invalid Baseline VO_{2MAX} the patient was to be invited to repeat the Baseline CPEX test within the 28-day period allowed between Screening and the start of study-drug dosing
 - v. After dosing commenced; if the centralized CPEX assessor deems the Baseline CPEX test to have been invalid or not within $\pm 20\%$ of the Screening CPEX then the patient was to remain in the study and the patient's Baseline CPEX result will be taken as the valid Baseline result
 - vi. All Baseline CPEX confirmations were to be received by study sites from the centralized CPEX assessor within a maximum of 48h.
- S. AEs were to be documented and recorded at each visit. All AEs (serious and non-serious, and related and non-related) were to be documented and recorded through the Follow-Up visit. Patients were to be followed for AEs until the final required protocol visit or until all drug-related toxicities and SAEs have resolved (or are considered chronic/stable).
- T. If an AE was determined to have been the result of a PEX-CIS Assay abnormality (e.g., false positive, false negative, measurement error), it will be deemed an ADE for the purpose of device reporting.
- U. Concomitant Medications was to be collected and recorded at each visit. All concomitant medications received up to and including 30 days prior to the start of study medication through the Follow-Up visit were to be recorded

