- R. Study-drug will be dispensed once the ECG Corelab confirms that the Baseline ECG meets the entry criteria. The first study-drug dose will be administered under the supervision of the study-site staff once the study-site staff confirm that the Baseline VO₂MAX is within $\pm 20\%$ of the Screening CPEX.

Note:

- If for any reason the ECG Corelab is not able to immediately confirm the ECG outcome, the patient will return home without receiving any dispensed study-drug. In such cases, once the ECG Corelab confirmation becomes available the patient will return to the site to collect the study-drug supply. The patient will then commence study-drug dosing (defined as Day 1).
 - All Baseline ECG confirmations will be received by study sites from the ECG Corelab within a maximum of 48h.
 - Before dosing has commenced; if the centralized CPEX assessor confirms the Baseline VO₂MAX is not within $\pm 20\%$ of the Screening CPEX then the patient will not enter the study
 - Before dosing has commenced; if the centralized CPEX assessor confirms an invalid Baseline VO₂MAX the patient will be invited to repeat the Baseline CPEX test within the 28-day period allowed between Screening and the start of study-drug dosing
 - After dosing has commenced; if the centralized CPEX assessor deems the Baseline CPEX test to have been invalid or not within $\pm 20\%$ of the Screening CPEX then the patient will remain in the study and the patient's Screening CPEX result will be taken as the valid Baseline result
 - All Baseline CPEX confirmations will be received by study sites from the centralized CPEX assessor within a maximum of 48h.
- S. AEs should be documented and recorded at each visit. All AEs (serious and non-serious, and related and non-related) will be documented and recorded through the Follow-Up visit. Patients must be followed for AEs until the final required protocol visit or until all drug-related toxicities and SAEs have resolved (or are considered chronic/stable).
- T. If an AE is determined to have been the result of a PEX-CIS Assay abnormality (e.g., false positive, false negative, measurement error), it will be deemed an ADE for the purpose of device reporting.
- U. Concomitant Medications should be collected and recorded at each visit. All concomitant medications received up to and including 30 days prior to the start of study medication through the Follow-Up visit will be recorded.

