3 ANALYSIS VARIABLES

3.1 Efficacy Variables

3.1.1 Primary efficacy variable

The primary endpoint of the study is the change from Baseline of VO₂MAX at the end of Period 2. Cardio-Pulmonary Exercise Testing (CPEX) was to be performed at Screening and repeated at Baseline (Day 1), at the end of Period 1 (Week 8) and the end of Period 2 (Week 16). Details of the exercise test performed and the resultant VO₂MAX evaluations were to be reported in the CRF. For entry into the study, the patient's VO₂MAX at Screening could not exceed 75% of the predicted age-adjusted value and the VO₂MAX at Baseline (Day 1) could not be outside $\pm 20\%$ of the Screening VO₂MAX value (if the centralized CPEX assessor deems the Baseline CPEX test is not within $\pm 20\%$ of the Screening CPEX after dosing with study medication has already commenced, the subject will remain in the study and the subject's Baseline CPEX result will be taken as the valid Baseline result, unless it is deemed invalid or if the CPEX test was administered after the start of study medication).

CPEX reports were to be validated by a centralized CPEX assessor.

The VO₂MAX at the Day 1 assessment will be regarded as Baseline unless the CPEX was reported to have been assessed after the start of study medication. If this situation arises, the VO₂MAX from Screening will be regarded as Baseline. Changes and percent changes from Baseline to the end of Period 2 VO₂MAX value will be derived:

$$\text{Change at Period 2} = \text{Period 2 VO}_{2\text{MAX}} - \text{Baseline VO}_{2\text{MAX}}$$

$$\text{Percent Change at Period 2} = (\text{Period 2 VO}_{2\text{MAX}} - \text{Baseline VO}_{2\text{MAX}}) / \text{Baseline VO}_{2\text{MAX}}$$

If the patient withdraws from the study early, but provides an unscheduled or early end-of-Period 2 VO₂MAX assessment then this VO₂MAX assessment will be used in the derivation of efficacy endpoints. Only if the unscheduled or early end-of-Period 2 VO₂MAX assessment is within ± 7 days of the intended target assessment (Period 2 target = Day 113), relative to Day 1, will the derived change in VO₂MAX be used in the primary analysis using the Completer Population (see section 7.1, below).

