4 ANALYSIS POPULATIONS

4.1.1 *Safety Population*

The Safety Population will include all patients who receive study drug.

4.1.2 *Modified Intention to Treat Population*

The Modified Intention to Treat Population (MITT) will include all patients who receive study drug and have at least one post-Baseline efficacy assessment.

4.1.3 *Completer Population*

The Completer Population will include all patients who receive study drug and complete all study procedures at Baseline, end of Period 1 and end of Period 2 and have their Period 2 CPEX assessment within 7 days of the target day of 113.

4.1.4 *Pharmacokinetic Population*

The Pharmacokinetic Population will include all patients who receive study drug and had at least one plasma sample collected.

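### For a dosed patient whose Day 1 CPEX is later judged invalid, two SAP statements make the rejected test the Baseline of the primary endpoint, against the protocol and a third SAP statement

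*SAP*

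**What the plan says.** The case is a patient who has started dosing when the centralized assessor reports that the Day 1 CPEX was invalid.

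- **Protocol 6.2 (footnote R) and 6.4:** "the patient will remain in the study and the patient's Screening CPEX result will be taken as the valid Baseline result". The same rule covers a Day 1 value found to be outside 20% of Screening.
- **SAP 2.2, schedule footnote R, note v:** the trigger is the same (invalid, or outside 20%) but the outcome is the opposite: "then the patient was to remain in the study and the patient's Baseline CPEX result will be taken as the valid Baseline result".
- **SAP 3.1.1, parenthesis in the first paragraph:** for a value outside 20%, Day 1 is kept, "unless it is deemed invalid or if the CPEX test was administered after the start of study medication". No replacement is named at that point.
- **SAP 3.1.1, derivation paragraph:** the Day 1 VO2MAX "will be regarded as Baseline unless the CPEX was reported to have been assessed after the start of study medication". Only in that event does the SAP switch to Screening.
- **SAP 3.1.2:** carries the primary rule over to the secondary VO2MAX endpoints.
- **SAP 2.2, footnote G i:** "A valid Screening CPEX was to be confirmed by the centralized CPEX assessor before the Baseline CPEX was done".

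SAP 12 lists three changes from the protocol. None concerns which test serves as Baseline.

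**The concern.** A programmer following the SAP literally could take Day 1 (note v or the derivation sentence) or set Baseline to missing (the parenthesis alone). The protocol gives Screening. Note v cannot safely be dismissed as a slip for Screening, because SAP 3.1.1 deliberately keeps Day 1 in the out-of-range case.

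The planned workflow allows the situation to arise. The first dose can be given at the Baseline visit once the ECG is confirmed and the site has made its own 20% check. Central CPEX validation is not a precondition and may take up to 48 hours.

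Baseline enters the change score directly. The results exposed are the Period 2 change and percent change (SAP 7.1), the Period 1 change (SAP 7.2.2) and the Week 8 snapshot t-test (SAP 10).

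A second, smaller point concerns a valid Day 1 test outside 20% of Screening. Here the SAP is consistent (Day 1) but differs from the protocol (Screening), and SAP 12 does not declare the departure.

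**Working it through.** **1. The rules side by side (patient already dosed)**

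| Source | Day 1 test invalid | Day 1 test valid, outside 20% |
|---|---|---|
| Protocol 6.2, 6.4 | Screening | Screening |
| SAP 2.2 note v | Day 1 | Day 1 |
| SAP 3.1.1 derivation sentence | Day 1 (no exception for invalidity) | Day 1 |
| SAP 3.1.1 parenthesis | not Day 1; no substitute named | Day 1 |

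The parenthesis names two exceptions, invalid and post-dose. The derivation paragraph resolves only the second.

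**2. The plan's own figures**

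Inputs from Protocol 8.2 and SAP 11: n = 30, SD of change 2.5, two-sided alpha 0.05, mean change 2.0 (Period 2) and 1.2 (Period 1). Exact one-sample t-test power (noncentral t, 29 df) is 98.9% for 2.0 (plan: above 95%) and 71.9% for 1.2 (plan: 72%). Both reproduce, and choosing one Baseline rule changes neither.

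**3. Shift in the mean change from one affected patient**

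The SAP 7.1 model has a single period level, so its LS mean at the covariate means equals the sample mean change. Replacing one patient's Baseline therefore moves it by exactly gap/30, where gap is the difference between the Day 1 and Screening values.

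The site check on Day 1 against Screening limits the gap to 20% of Screening, if site and central values agree; footnote G ii says "this was to be calculated by study-site staff in order to allow a decision on patient inclusion". The documents give no typical Screening VO2MAX, so 15 to 22 mL/kg/min is assumed.

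| Screening (assumed) | Gap = 0.20 × Screening | Gap/30 | Share of 2.0 | Share of 1.2 |
|---|---|---|---|---|
| 15 | 3.0 | 0.100 | 5.0% | 8.3% |
| 18 | 3.6 | 0.120 | 6.0% | 10.0% |
| 22 | 4.4 | 0.147 | 7.3% | 12.2% |

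A low Day 1 value raises the estimated change and a high one lowers it. The planned standard error is 2.5/√30 = 0.456, so the shift is 0.22 to 0.32 standard errors.

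**4. Percent change**

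Assume Screening 18 and a Period 2 value of 18 + 2.0 = 20.0.

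- Screening rule: 2.0/18 = 11.1%.
- Day 1 rule, Day 1 = 14.4: 5.6/14.4 = 38.9%. The difference is +27.8 points, or +0.93 in the mean of 30.
- Day 1 rule, Day 1 = 21.6: −1.6/21.6 = −7.4%. The difference is −18.5 points, or −0.62 in the mean of 30.

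Over Screening 15 to 22 the ranges are +0.91 to +0.94 and −0.61 to −0.63.

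**5. Effect through the covariate**

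The primary ANCOVA was simulated 4,000 times with n = 30, assumed baseline mean 18 and SD 3, and change SD 2.5, replacing one Baseline by a value 20% lower. The LS mean moved by gap/30 in every run. The ratio of standard errors had median 1.03 (5th to 95th percentile 0.95 to 1.13). The covariate role thus affects mainly precision.

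**6. Period 2 minus Period 1**

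Baseline cancels from the unadjusted difference (shift 0). It need not cancel exactly from the contrast planned in SAP 7.2.1, which adjusts for period-mean plasma perhexiline (PEX).

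**7. What the 20% does not bound**

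These are gaps between two rules, not limits on measurement error. With assumed values Screening 18, true Day 1 value 19.8 and an invalid reading of 14.4, the site check is passed (14.4/18 = 0.80), yet the error is 5.4, or 30% of Screening.

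**The case against.** The strongest reply is that only note v, a footnote in an overview section, expressly keeps a rejected test. The derivation sentence is silent on validity. Read with the parenthesis and the statement that CPEX reports are centrally validated, SAP 3.1.1 could be taken to exclude the invalid test and to imply Screening. That is a reasonable reading, but it is nowhere stated, and note v still contradicts it.

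Other points, and what stands of each:

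- **Small and conditional effect.** This stands. The shift needs a test at the edge of the 20% check, its direction is unknown, and the count may be zero. Lowering the assumed Period 2 change from 2.0 to 1.85 would reduce power only from 98.9% to 97.5%. No type I error inflation is shown.
- **The Completer Population may remove such patients.** SAP 4.1.3 requires that they "complete all study procedures at Baseline, end of Period 1 and end of Period 2", but does not say whether a rejected CPEX counts as completed. The MITT repeat has no such condition.
- **It can be settled before lock.** Agreed: SAP 1 says "Any revisions to the SAP (both alternative and additional methods) will be made prior to database lock". That is an opportunity to correct the text; it does not supply the rule.
- **Protocol 4.6** makes discontinuation mandatory for some patients with out-of-range or unrepeated tests, without limiting this to the time before dosing, while 6.2 and 6.4 keep the dosed patient in. This concerns who stays in the study, not which test is Baseline, but those passages also need reconciling.
- **Protocol version.** The SAP cites version 11, and the protocol text available for review shows no version number. This caveat touches only the undeclared departure for valid out-of-range tests.

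**Conclusion.** The concern holds. For an invalid Day 1 CPEX in a dosed patient, note v expressly, and the SAP 3.1.1 derivation sentence by its literal terms, make the rejected test the Baseline of the primary endpoint. The protocol says Screening, and the SAP 3.1.1 parenthesis says not Day 1. The contradiction is certain on the text.

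Its numerical effect is modest: at most 0.10 to 0.15 mL/kg/min in the mean change per affected patient. This rests on 30 completers, an assumed Screening VO2MAX of 15 to 22, and agreement between site and central values. It should be fixed because it concerns the definition of the primary endpoint and is cheap to correct, not because a material bias has been shown.

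**What to change.** Before database lock, and before the Week 8 snapshot if that has not yet been run:

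1. State one rule in SAP 2.2 note v and in both paragraphs of SAP 3.1.1: an invalid or post-dose Day 1 CPEX is never Baseline and is replaced by the centrally confirmed valid Screening CPEX. SAP 3.1.2 then follows.
2. State in SAP 4.1.3 whether such a patient belongs to the Completer Population.
3. For a valid Day 1 test outside 20% of Screening, either adopt the Baseline rule in Protocol 6.2 and 6.4, or keep the SAP rule and declare the departure in SAP 12.
4. Reconcile Protocol 4.6 with 6.2 and 6.4 on whether these patients remain in the study.
5. Only if affected patients exist, list them in the CSR and show the other Baseline rule as a sensitivity analysis.

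The statistical changes (items 1 to 3 and 5) need SAP wording, plus one listing and one sensitivity table if item 5 applies. Item 4 is a separate clarification of the protocol text. No new data are needed.
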